Participants will receive their first Moderna mRNA-1273 COVID-19 vaccine dose in the community. Their second Moderna mRNA-1273 dose will be provided by the study (100 µg [0.5 mL] to be administered IM 28 days after their first dose).

NOTE: These participants may enter the study before or after their first vaccine dose.

Participants without prior history of SARS-CoV-2 infection

Participants will receive the following study-provided regimen: Moderna mRNA-1273 COVID-19 vaccine, 100 µg (0.5 mL) to be administered IM at Entry and Day 28.

c. Section 3.0 Study Design

The last sentence of the second paragraph: “Participants will have blood collected and immune responses measured before the first vaccine dose (if feasible), and before the second dose of vaccine (e.g., 28 days later for Moderna vaccine and 21 days later for Pfizer vaccine if given in the community) (**if feasible**), and 56 (**if feasible**), 140, 365, and 730 days after **their first vaccine dose** (Figure 3.0-1).”

d. Section 4.2 Exclusion Criterion 4.2.2

This criterion was revised as follows: “For participants who are in, or who have completed, the ACTIV-2/A5401 trial: Self-report of receipt of the ~~second~~ **first** dose of an mRNA-based COVID-19 vaccine **140 days or more before A5404 enrollment.**”

e. Section 5.1.1 Regimen and Duration

Participants will receive the following study-provided regimen: Moderna mRNA-1273 COVID-19 vaccine, 100 µg (0.5 mL) to be administered intramuscularly (IM) at **Entry** and Day 28.

Or

Participants will receive a two-dose series of a community-provided mRNA-based COVID-19 vaccine that has received FDA EUA or FDA approval.

NOTE: Participants who receive a community-provided mRNA-based COVID-19 vaccine may receive their **first and second** COVID-19 vaccine dose(s) before study entry.

Or

Participants will receive (or have recently received) a community-provided Moderna mRNA-1273 COVID-19 vaccine at (or before) **Entry** and study-provided Moderna mRNA-1273 COVID-19 vaccine, 100 µg (0.5 mL) to be administered intramuscularly (IM) at at least 28 days apart.

f. Section 6.1, Table 6.1-3

The title of this section was changed to, “~~Community Provided mRNA-based COVID-19 Vaccine~~ Schedule of Evaluations for ACTIV-2/A5401 Participants **who Received First Dose of a Community-Provided mRNA-based COVID-19 Vaccine Before Entry or Will Receive First Dose After Entry**”

g. Section 6.1, Table 6.1-4 was added:

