2.1 Study Design

A5404 is a phase IV, open-label, sub-study of ACTIV-2/A5401 aiming to evaluate how prior investigational therapy for COVID-19 versus comparator (placebo or active comparator) affects vaccine response. This is a non-randomized study designed to have reasonable precision to estimate the difference in immune response between those with versus without prior select investigational therapy for COVID-19. Results will be interpreted in the context of available information from outside the study when analyses are completed.

The study will enroll a target of 70 participants from each ACTIV-2/A5401 select therapy group (comprised of individuals exposed to active treatment and individuals exposed to the corresponding placebo or active comparator). In addition, up to 70 individuals without prior history of SARS-CoV-2 infection will be enrolled based on vaccine supply at each A5404 site. The total sample size will depend on how many therapies are selected from ACTIV-2/A5401. The ratio of participants with active therapy exposure versus corresponding comparator exposure in ACTIV-2/A5401 is also unknown a priori, as the randomization ratio for ACTIV-2/A5401 study depends on the number of agents concurrently enrolling. If the target sample of 70 participants for a select therapy group is not able to be met from Phase II participants in the ACTIV-2/A5401 trial, then enrollment will open to participants from the respective Phase III group in ACTIV-2/A5401.

Eligible participants will receive mRNA COVID-19 vaccine in one of three ways:

Cohort 1: ACTIV-2/A5401 participants

Participants will receive one of the following regimens:

Cohort 1a: Moderna mRNA-1273 COVID-19 vaccine, 100 µg (0.5 mL) to be administered intramuscularly (IM) at Entry and Day 28. Both doses will be provided by the study.

Or

Cohort 1b: Participants will receive a two-dose series of a community-provided mRNA-based COVID-19 vaccine that has received FDA EUA or FDA approval (e.g., Moderna or Pfizer). Vaccine will not be provided by the study.

NOTE: These participants may enter the study before their first vaccine dose, after their first vaccine dose, or after their second vaccine dose.

Or

Cohort 1c: Participants will receive their first Moderna mRNA-1273 COVID-19 vaccine dose in the community. Their second Moderna mRNA-1273 dose will be provided by the study (100 µg [0.5 mL] to be administered IM 28 days after their first dose).

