NOTE: These participants may enter the study before or after their first vaccine dose.

Or

Cohort 2: Participants without prior history of SARS-CoV-2 infection

Participants will receive the following study-provided regimen: Moderna mRNA-1273 COVID-19 vaccine, 100 µg (0.5 mL) to be administered IM at Entry and Day 28.

All participants will have blood collected and immune responses measured before the first vaccine dose (if feasible), and before the second dose of vaccine (e.g., 28 days later for Moderna vaccine and 21 days later for Pfizer vaccine if given in the community) (if feasible), and 56 (if feasible), 140, 365, and 730 days after their first vaccine dose.

We initially intended to conduct the primary analysis separately within each select ACTIV-2/A5401 therapy group. However, due to a lower than anticipated accrual, we revised the plan to instead conduct the primary analysis combining participants from select ACTIV-2/A5401 therapy groups. The primary analysis will occur after the last enrolled participant from ACTIV-2/A5401 has reached the Day 140 study visit.

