3.2 Secondary Outcome Measures

- 3.2.1** Relative pre-vaccine to post-vaccine change in NAb response defined as the ratio of post-vaccine level/pre-vaccine level. The pre-vaccine NAb measurement will be obtained before the first dose of the vaccine and the post-vaccine measurement will be obtained at least 56 days after the first dose of the vaccine. (Objective 2.3.1.1)
- 3.2.2** New Grade 3 or higher AE, or SAE, or AE leading to change or discontinuation in vaccine receipt from first dose of the mRNA-based COVID-19 vaccine and through 140 days after the first dose of vaccine. (Objective 2.3.2.1)
- 3.2.3** Grade 1 or higher allergic reaction from first dose of the mRNA-based COVID-19 vaccine through the visit 56 days after the first dose of the vaccine. (Objective 2.3.2.1)
- 3.2.4** Grade 2 or higher injection site reaction from first dose of the mRNA-based COVID-19 vaccine through the visit 56 days after the first dose of the vaccine. (Objective 2.3.2.1)
- 3.2.5** Relative pre-vaccine to post-vaccine change in NAb response defined as the ratio of post-vaccine level/pre-vaccine level by received vaccine, i.e., Moderna versus Pfizer. The pre-vaccine NAb measurement will be obtained before the first dose of the vaccine, and the post-vaccine measurement will be obtained at least 56 days after the first dose of the vaccine. (Objective 2.3.1.1)

4 General Considerations

The aim of this study is to describe immunologic responses to mRNA-based SARS-CoV-2 vaccine among individuals who previously received investigational therapy in ACTIV-2/A5401 for SARS-CoV-2 infection in comparison to individuals who received a placebo. As ACTIV-2/A5401 is expected to change from using a placebo control to an active control, this study's aim will also evolve to describe immunologic responses to mRNA-based SARS-CoV-2 vaccine among individuals who previously received investigational therapy in ACTIV-2/A5401 for SARS-CoV-2 infection in comparison to individuals who received an active control.

Estimates and confidence intervals for NAb will be obtained by using a log base 10 transformation on the PSV values, then using linear regression with an indicator variable for prior select COVID-19 therapy exposure versus placebo using standard methods, assuming that the \log_{10} NAb responses are approximately normally distributed within exposure group.

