4.1.2 Safety Set

All enrolled participants who received the first dose of vaccine

Subgroups or subpopulations of interest

- 4.1.3** Subgroups defined by levels of sex, if sample size permits
- 4.1.4** Subgroups defined by levels of race/ethnicity, if sample size permits

5 Estimands

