5.3 Secondary Safety Estimand

Secondary Objective 2.3.2.1: To explore the safety of mRNA-based COVID-19 vaccines among participants with prior COVID-19 who received investigational therapy or its comparator for COVID-19 and persons who are SARS-CoV-2 naïve.
	
Estimand description	Occurrence of adverse events up to 56 and 140 days after receiving the first dose of an mRNA-based COVID-19 vaccine among individuals receiving at least one dose of the vaccine with and without prior history of COVID-19.
Treatment	
Cohort 1a: Moderna mRNA-1273 COVID-19 vaccine, 100 µg (0.5 mL) to be administered intramuscularly (IM) at Entry and Day 28. Both doses will be provided by the study.
 
Or
 
Cohort 1b: Participants will receive a two-dose series of a community-provided mRNA-based COVID-19 vaccine that has received FDA EUA or FDA approval (e.g., Moderna or Pfizer). Vaccine will not be provided by the study.
 
NOTE: These participants may enter the study before their first vaccine dose, after their first vaccine dose, or after their second vaccine dose.
 
Or
 
Cohort 1c: Participants will receive their first Moderna mRNA-1273 COVID-19 vaccine dose in the community. Their second Moderna mRNA-1273 dose will be provided by the study (100 µg [0.5 mL] to be administered IM 28 days after their first dose).
 
Or
 
Cohort 2: Participants will receive the following study-provided regimen: Moderna mRNA-1273 COVID-19 vaccine, 100 µg (0.5 mL) to be administered IM at Entry and Day 28.

Target population	Analysis sets
Individuals who received an mRNA-based COVID-19 vaccine with and without a prior history of COVID-19.	Safety Set (all enrolled participants who received at least one dose of vaccine)
Variable	Outcome measures
Occurrence of an adverse event up to 56 and 140 days after first dose of an mRNA-based COVID-19 vaccine.	
New Grade 3 or higher AE, SAE, or AE leading to change or discontinuation in vaccine receipt from first dose of the mRNA-based COVID-19 vaccine and through 140 days after the first dose of the vaccine.
 
Grade 1 or higher allergic reaction from first dose of the mRNA-based COVID-19 vaccine through the visit 56 days after the first dose of the vaccine.
 
Grade 2 or higher injection site reaction from first dose of the mRNA-based COVID-19 vaccine through the visit 56 days after the first dose of the vaccine.

Handling of intercurrent events	Handling of missing data

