
Population-level summary measure
 
Probability of having at least one Grade 3 or higher adverse event following first dose of vaccine through 140 days after the first vaccine dose.
 
Probability of having a Grade 1 or higher allergic reaction from the first dose of vaccine through 56 days after the first vaccine dose.
 
Probability of having a Grade 2 or higher injection site reaction from first dose of vaccine through 56 days after the first vaccine dose.
	
Analysis approach
 
Proportions and confidence intervals described below will be estimated for:
 
 (1) Participants exposed to AZD7442 IM or IV, BRII-196+BRII 198 IV, SAB 185 (3,840 or 10,240 units/kg), BMS 096414+BMS 986413 subcutaneous or Camostat in ACTIV-2/A5401 (2) Participants exposed to placebo in ACTIV-2/A5401 (3) Participants without prior history of COVID-19 
(note that for the safety analysis, Camostat is considered an active agent)
 
Proportion of participants with at least one Grade 3 or higher adverse event through 140 days after the first vaccine dose and exact 95% confidence interval.
 
Proportion of participants with a Grade 1 or higher allergic reaction from the first dose of vaccine through 56 days after the first vaccine dose and exact 95% confidence interval.
 
Proportion of participants with a Grade 2 or higher injection site reaction from first dose of

	vaccine through 56 days after the first vaccine dose and exact 95% confidence interval.
--	---

Supplemental Analyses

If sample size permits, analyses will be carried out in subgroups defined by levels of sex and levels of race/ethnicity.

6 Analysis of other secondary objectives

6.1.1 Relative pre-vaccine to post-vaccine change in NAb response defined as the ratio of post-vaccine level/pre-vaccine level by received vaccine, i.e., Moderna versus Pfizer. The pre-vaccine NAb measurement will be obtained before the first dose of the vaccine, and the post-vaccine measurement will be obtained at least 56 days after the first dose of the vaccine. (Objective 2.3.1.1)

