7.6 Adverse Events

- Summary of post-entry reportable adverse events (per section 7.0 of study protocol)
- Listing of all adverse events by participant (public participant identifier)
- Summary of post-entry grade 3 or higher AE, SAE, or AE leading to a change or discontinuation in vaccine receipt from first dose of the mRNA-based COVID-19 vaccine through 140 days after the first vaccine dose

- Summary of post-entry grade 1 or higher allergic reactions from first dose of the mRNA-based COVID-19 vaccine through 56 days after the first vaccine dose
- Summary of post-entry grade 2 or higher infection site reactions from first dose of the mRNA-based COVID-19 vaccine through 56 days after the first vaccine dose

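### The 140-day Grade 3+ adverse event proportion keeps participants who enrolled after vaccination in its denominator from dose 1, with no rule for their unobserved pre-entry time

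*SAP*

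**What the plan says.** - **Outcome.** SAP 3.2.2 defines a composite: "New Grade 3 or higher AE, or SAE, or AE leading to change or discontinuation in vaccine receipt from first dose", running through Day 140. The proportion in SAP 5.3 is narrower: participants with at least one "Grade 3 or higher adverse event through 140 days after the first vaccine dose and exact 95% confidence interval". SAP 7.9 repeats the narrower form.
- **Denominator.** The Safety Set (SAP 4.1.2) is "All enrolled participants who received the first dose of vaccine", whatever the entry date.
- **Late entry.** For Cohort 1b, SAP 5.3 notes: "These participants may enter the study before their first vaccine dose, after their first vaccine dose, or after their second vaccine dose". SAP 2.1 lets Cohort 1c enter before or after the first dose. Under Letter of Amendment #1, item 3d (exclusion criterion 4.2.2), a person is excluded only if the first dose was received "140 days or more before A5404 enrollment".
- **Naive group.** Cohort 2 receives study vaccine "to be administered IM at Entry and Day 28" (SAP 2.1), so its members are followed from dose 1.
- **Events summarised.** SAP 7.6 lists: "Summary of post-entry grade 3 or higher AE, SAE, or AE leading to a change or discontinuation in vaccine receipt from first dose". SAP 5.3 and 7.9 contain no post-entry restriction.
- **Missing data.** SAP 5.3 uses whatever was observed before early discontinuation and acknowledges that this assumes no later event. A sensitivity analysis counts early discontinuers as having an event. Late entry has no corresponding rule.
- **History.** SAP 1.2 records that version 3.0 dropped the Retrospective Safety Analysis Set as not relevant any more. SAP 7.5 still summarises vaccination before entry and the days from first vaccine to entry.

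**The concern.** A proportion labelled as the risk from dose 1 to Day 140 needs everyone in the denominator to be observed over that span, or a stated rule for those who were not. A person who enters on Day 100 counts as a full binomial trial but is followed prospectively for only 40 of the 140 days. If the post-entry restriction in 7.6 governs, the first 100 days contribute no events. If 5.3 governs, those days contribute only what can be recovered at entry.

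The problem is one-sided. It can affect safety groups (1) active therapy and (2) placebo, both drawn from ACTIV-2/A5401. It cannot affect group (3), the naive participants. The three proportions are reported side by side, so any understatement falls only on the prior-COVID groups. With 43 participants enrolled in total (SAP 2.4), a few late entrants would be a visible share of a group.

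**Working it through.** The plan states no safety rate, safety sample size or safety interval, so there is no figure of its own to reproduce.

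**Inputs from the documents:** window 140 days; latest entry Day 139; 43 enrolled, with neither the split by safety group nor the number of late entrants given.

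**Assumptions:** true 140-day risk r = 10%; a share f of the group enters on day E; pre-entry events are not counted.

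**Step 1. Unobserved share of the window = E/140.** Day 14: 10%. Day 28: 20%. Day 56: 40%. Day 70: 50%. Day 100: 71%. Day 139: 99%.

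**Step 2. Expected observed proportion, constant hazard.** h = -ln(1 - r)/140 = 0.10536/140 = 0.000753 per day. Observed = (1 - f) × r + f × [1 - exp(-h(140 - E))]. The bracket is 5.13% for E = 70 and 2.97% for E = 100.

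| f | E | Calculation | Observed |
|---|---|---|---|
| 20% | 70 | 0.8 × 10% + 0.2 × 5.13% | 9.0% |
| 30% | 100 | 0.7 × 10% + 0.3 × 2.97% | 7.9% |
| 50% | 100 | 0.5 × 10% + 0.5 × 2.97% | 6.5% |

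A naive group with the same true risk would have an expectation of 10%.

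**Step 3. Front-loaded risk.** Suppose half the risk (5%) falls by Day 42 and the rest is spread evenly over the remaining 98 days. A Day 100 entrant then shows 5% × 40/98 = 2.04%. For f = 30% the observed value is 7.0% + 0.6% = 7.6%; for f = 50% it is 5.0% + 1.0% = 6.0%.

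**Step 4. Exact limits (Clopper-Pearson), assumed groups.** With no events the upper limit is 1 - 0.025^(1/n).
- Group of 14 with 5 late entrants, no events: 0/14 gives 23.2%; the 9 observed from dose 1 give 0/9, 33.6%.
- Group of 20 with 10 late entrants, one event among those observed from dose 1: 1/20 = 5.0% (0.1% to 24.9%) against 1/10 = 10.0% (0.3% to 44.5%).

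**Step 5. Does the interval still cover the true risk?** Let q be the share of a late entrant's risk that falls before entry, so that expected observed risk = p(1 - fq). At p = 10% and N = 10, 20 or 30, coverage stays at or above 98.7% in the scenarios run. At p = 20% and N = 20, it falls from 97.8% (fully observed) to 92.2% with f = 0.5, q = 0.8, and to 64.2% with f = 0.75, q = 1.

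**The case against.** The strongest reply is that 7.6 is a list of report contents and not the estimand. SAP 5.3 and 7.9 count from dose 1. The schedule for people who enter after both doses (Letter of Amendment #1, Table 6.1-4) includes medical history and a Vaccine Symptom Screen at entry, and item 3l drops the screen only when entry is more than 14 days after a dose. The adverse event rules in protocol section 7.0, to which 7.6 refers, are not in the text available for review. A reader might infer that late entrants can register no pre-entry event at all; the documents do not support that. What stands is that 5.3 and 7.6 disagree on when counting starts, and that beyond 14 days no symptom screen covers the earlier doses.

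Three other strong readings also fail.

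- **That the prior-COVID groups will look safer than the naive group.** This is a direction of possible bias, not a result. The objective is exploratory, no between-group safety contrast is planned, and dropping the Retrospective Safety Analysis Set may mean that few people entered late. SAP 7.5 leaves that unresolved.
- **That the exact intervals are invalid.** Step 5 shows that under-coverage depends on the risk, the group size and the late-entry share. The 0/9 contrast also discards real follow-up: a Day 70 entrant is observed for half the window.
- **That people who completed both doses should leave the denominator for vaccine discontinuation.** They did not discontinue, so counting them as non-events is correct. Any distortion there is selection into the study. That component is also absent from the proportion in 5.3.

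The illustrations have limits too. Cohort 1c receives its second dose on study about 28 days after the first, so late entry there leaves roughly 28/140 = 20% of the window unobserved; Day 70 to 100 entry fits only Cohort 1b. In a group of 14, a fall from 10% to between 9.0% and 6.0% is 14 × 0.010 to 14 × 0.040, or about 0.1 to 0.6 of a participant, which is small beside the interval width.

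**Conclusion.** The concern holds in a limited form. The plan puts late entrants in a dose-1-to-Day-140 denominator, treats their pre-entry time wholly or largely as event-free, and has neither a rule nor a sensitivity analysis for it, although it has both for early withdrawal. If there are late entrants, the affected prior-COVID proportions are biased downward and the naive proportion is not. A descriptive purpose does not remove this, because the label still claims observation from dose 1.

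The amount is unknown. The figure of 6.5% to 9.0% for a true 10% rests on an assumed risk, a constant hazard, assumed late-entry shares and entry days, and no pre-entry capture; front-loaded risk takes the low end to 6.0%. If nobody entered late, there is no bias. The downward shift is the main harm. The exact intervals count partly observed people as full trials, but they do not necessarily under-cover.

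Separately, the proportion in 5.3 and 7.9 covers Grade 3+ events only, whereas 3.2.2 and 7.6 describe the composite.

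**What to change.** In SAP 5.3, 7.6 and 7.9:

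1. Report the 140-day proportion and exact 95% interval among participants who entered on or before their first dose.
2. Show those who entered after dose 1 or dose 2 separately, with events per post-entry person-time. Alternatively, include them in a cumulative-incidence estimate with delayed entry at the enrolment date, stating the assumption that entry time is unrelated to risk.
3. Use one counting start in 5.3, 7.6 and 7.9, and say how events between dose 1 and entry are treated.
4. State whether the reported proportion is Grade 3+ events only or the full 3.2.2 composite.

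The timing data are already needed for SAP 7.5, so no new collection is required. The cost is revised wording, one more table, smaller Cohort 1 denominators and wider intervals. SAP 1.2 says the final analysis report was conducted under version 3.0, so the restricted proportion may have to be added as a supplementary analysis and labelled post hoc.

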
Population-level summary measure
 
Geometric mean neutralizing antibody levels at 140 days after first dose of an mRNA-based COVID-19 vaccine.
	
Analysis approach
 
We will report the geometric mean NAb levels among each group:
 
 (1) Participants exposed to AZD7442 IM or IV, BRII-196+BRII 198 IV, SAB 185 (3,840 or 10,240 units/kg), BMS 096414+BMS 986413 subcutaneous in ACTIV-2/A5401 (2) Participants exposed to placebo in ACTIV-2/A5401 (3) Participants exposed to placebo or Camostat Oral in ACTIV-2/A5401 
Ratio of geometric mean neutralizing antibody levels comparing those who received select investigational therapy (AZD7442 IM or IV, BRII-196+BRII-198 IV, SAB 185 (3,840 or 10,240 units/kg), BMS 096414+BMS 986413 subcutaneous in ACTIV-2/A5401) relative to placebo at Day 140 study visit, together with corresponding 95% confidence interval. We will use the log base 10 scale for the analysis of NAb measurements and report the anti-logged estimates and confidence intervals. We assume that the NAb responses are approximately normally distributed on the log base 10 scale and so confidence intervals can be calculated using standard methods.
 
The analysis will be repeated comparing those who received select investigational therapy (AZD7442 IM or IV, BRII-196+BRII-198 IV, SAB 185 (3,840 or 10,240 units/kg), BMS 096414+BMS 986413 subcutaneous in ACTIV-2/A5401) relative to placebo or Camostat.

Supplemental Analyses

To allow for the possibility that the distribution of time from receipt of select investigational therapy or placebo to the first dose of vaccine may differ, an analysis adjusted for this time may also be undertaken if sample size permits.

If sample size permits, the same analyses will be carried out in subgroups defined by levels of sex, race/ethnicity, and mRNA vaccine (Moderna or Pfizer).

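### SAP 5.3 sets a Moderna-only naive group beside prior-COVID groups that may include Pfizer recipients, with no safety split by product, so a product difference could be misread as an effect of prior COVID-19

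*SAP*

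**What the plan says.** The Treatment row of SAP 5.3 gives the naive cohort (Cohort 2) one vaccine: "Participants will receive the following study-provided regimen: Moderna mRNA-1273 COVID-19 vaccine". Cohorts 1a and 1c, both prior-COVID, are also Moderna only. Cohort 1b, also prior-COVID, is different: its members receive a "community-provided mRNA-based COVID-19 vaccine that has received FDA EUA or FDA approval (e.g., Moderna or Pfizer").

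The Analysis approach in 5.3 begins "Proportions and confidence intervals described below will be estimated for" and names three groups: (1) active agents, with Camostat counted as active; (2) placebo; and ("3) Participants without prior history of COVID-19"). Each group gets a proportion with an exact 95% confidence interval for Grade 3 or higher adverse events through Day 140, and for allergic and injection site reactions through Day 56.

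The only safety subgroups are in the Supplemental Analyses: "If sample size permits, analyses will be carried out in subgroups defined by levels of sex and levels of race/ethnicity". SAP 7.6 and 7.9 add no split by vaccine. The primary antibody estimand in SAP 5.1 does have one, planning "subgroups defined by levels of sex, race/ethnicity, and mRNA vaccine (Moderna or Pfizer"), and SAP 6.1.1 compares Moderna with Pfizer on antibody change.

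**The concern.** Every Pfizer recipient in this study has had COVID-19, and every naive participant receives Moderna. Product is therefore tied to prior-COVID status by design. The safety objective covers both populations, and the estimand is described in terms of people with and without prior COVID-19, so the naive column will naturally be read against the other two.

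If one product causes more Grade 2 or higher injection site reactions, for example, the naive proportion will sit above or below the prior-COVID proportions even if prior infection has no effect. The exact intervals give no warning of this, because they describe sampling error and not a difference in product mix. The SAP treats product as worth separating for antibody response. Yet safety is the only one of its three estimands that includes the Moderna-only naive group, and it is not split by product.

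**Working it through.** **The plan's own figures.** The SAP states no expected rate or precision for any safety proportion. Its only precision figures are for neutralizing antibody in SAP 2.4. They reproduce as 10^(±t × SD × √(2/35)) with 68 degrees of freedom: SD 0.5 gives (0.63, 1.58) at 90% and (0.58, 1.73) at 95%. They do not bear on this point.

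**Inputs from the documents.** Cohort 2 is Moderna only; Cohort 1b may be Moderna or Pfizer; Cohorts 1a and 1c are Moderna only (SAP 2.1 and 5.3). Total enrolment is 43 (SAP 2.4), with no breakdown by safety group or by product.

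**Inputs assumed.** The Pfizer share f of a prior-COVID group, and the reaction risks pM (Moderna) and pP (Pfizer). The documents give none of these.

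**Naive versus prior-COVID.** Suppose prior COVID-19 and prior therapy have no effect on reactions and all doses are observed equally well. The naive group's risk is pM. A prior-COVID group's risk is (1 − f) × pM + f × pP. The apparent gap is

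pM − [(1 − f) × pM + f × pP] = f × (pM − pP).

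For example, with pM = 20%, pP = 10% and f = 50%, the prior-COVID risk is 0.5 × 20% + 0.5 × 10% = 15%, a gap of 5 points.

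| Assumed Pfizer share f | Gap if products differ by 10 points | Gap if products differ by 20 points |
|---|---|---|
| 0% | 0 | 0 |
| 25% | 2.5 | 5 |
| 50% | 5 | 10 |
| 75% | 7.5 | 15 |

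The gap is zero if nobody received Pfizer or if the products do not differ. Its sign depends on which product has the higher risk.

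**Active versus placebo.** The same algebra gives (f_placebo − f_active) × (pM − pP). Equal shares give zero. An assumed 20-point difference in share gives 0.20 × 10 = 2 points to 0.20 × 20 = 4 points.

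**Scale of sampling error.** Clopper-Pearson 95% intervals at assumed counts: 2/10 gives 2.5% to 55.6%; 3/15 gives 4.3% to 48.1%; 4/20 gives 5.7% to 43.7%.

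**Do the listed outputs already separate product from prior COVID-19?** SAP 7.5 counts Moderna and Pfizer recipients but does not link them to events. The opening of SAP 7 groups tables by active therapy, placebo, or the three groups of Section 2.4. Those three groups omit naive participants, and one of them pools Camostat with placebo, whereas 5.3 counts Camostat as active. The 7.5 counts therefore need not show the product mix of the 5.3 groups. SAP 7.6 lists adverse events by participant but does not mention product.

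**Would a Moderna-only row be a clean comparison?** Not entirely. Under the Letter of Amendment's revision of protocol Section 6.3.8, no symptom screen is collected for community doses when the participant enrols more than 14 days after them, and the SAP 7.6 summaries are of post-entry events. Naive participants receive both doses on study, with a scheduled follow-up after each. Some community Moderna doses in groups 1 and 2 will therefore be less well observed than any naive dose.

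**The case against.** The strongest reply is that SAP 5.3 plans no comparison. It estimates a proportion for each group, with no difference, ratio or test; the study is descriptive and non-randomized; and nothing in the SAP calls the naive group a reference. Pooling the products also fits the stated target population, which is people who received any mRNA vaccine. This stands in part. The SAP makes no biased claim, so the risk is one of misreading. But the same outcomes are reported for groups defined by prior COVID-19, and readers will compare them.

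A reader might go further and infer that product mix also distorts active versus placebo, so that it could pass for an effect of prior therapy. The documents do not support that. Both groups have the same Cohort 1 options, and the term is zero unless their Pfizer shares differ. Chance imbalance is possible in small groups but is not shown.

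A reader might also infer that no planned table could separate product from prior COVID-19. That cannot be established. SAP 1.1 places detailed table outlines in an Analysis Implementation Plan that is not among the documents; what can be said is that the SAP requires no such table.

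Two further objections stand. The assumed gaps lie well inside the exact intervals. And a full split by product would be thin: 43 participants over five cells (two products in each of groups 1 and 2, plus naive) average 43/5 = 8.6 per cell, and 0/5 gives an interval of 0% to 52%.

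**Conclusion.** The point holds as one about how the naive column can be read. By design, product is tied to naive status, and the safety section does not require a display that separates the two. A product difference in reactions could therefore be misread as an effect of prior COVID-19.

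The size cannot be determined from the documents. It is the Pfizer share times the risk difference: 2.5 to 15 percentage points for shares of 25% to 75% and risk differences of 10 to 20 points, all of them assumptions. If no Pfizer recipients or no naive participants enrolled, or if the products carry equal risk, the point has no effect. It concerns a descriptive secondary objective and leaves the antibody analyses untouched.

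**What to change.** In SAP 5.3 (Analysis approach) and 7.9:

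- Beside each all-product proportion, add a descriptive Moderna-only row with its exact 95% interval for groups 1, 2 and 3.
- Give Moderna and Pfizer counts for each 5.3 safety group, with Camostat counted as active and the naive group included.
- Flag, or count separately, participants whose doses preceded entry and had no symptom screen. Do not label the Moderna-only row like-for-like, because this difference in ascertainment remains.
- Show Pfizer recipients in groups 1 and 2 as plain counts of events if cells are very small.

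The cost is SAP wording and a few table rows. Product is already documented for community vaccination and summarized under SAP 7.5, so no new data are needed. SAP 1.2 says the final report was produced under version 3.0, so the rows may have to be added as a supplementary table. The downside is smaller cells: dropping from 4/20 to 3/15, for instance, widens the interval from 6% to 44% to 4% to 48%, and smaller cells fare worse. With at most 43 participants in all, the rows can only be descriptive.
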